### 5.4.1.5 Name and Description of Each Non-Investigational Medicinal Drug (NIMP)

1. Cefuroxime can be administered subconjunctivally at 0.5ml normal saline, or 125mg in 1.0mL normal saline according to local practice or cefazolin or vancomycin antibiotic given at usual dose at end of surgery (standard dose as prophylaxis for post-operative infection)

2. Long acting steroid in the sub-tenon space following sclerotomy closure (see details in CNGA3 ATIMP Management Plan).

3. Betamethasone can be administered subconjunctivally at 2.mg- 5mg in 0.5mL, according to local practice, or dexamethasone can be administered subconjunctivally at 1.5mg-2.0mg in 0.5mL, according to local practice at end of surgery (standard dose as prophylaxis for post-operative inflammation)

4. Chloramphenicol 0.5% or ofloxacin (topical antibiotic) 4 times daily for 7 days following ATIMP administration

5. Dexamethasone 0.1% (topical steroid) or topical prednisolone drops 1.0% should be administered 4 times daily for 4 weeks following ATIMP administration

4 and 5 above will be administered to minimise inflammation and protect against infection postoperatively.

6. Omeprazole:

- In children aged up to 15 weighing 5 kg to less than 10 kg (11 lb to less than 22 lb): 5 mg taken once per day
- In children aged up to 15 weighing 10 kg to less than 20 kg (22 lb to less than 44 lb): 10 mg taken once per day
- In children aged up to 15 weighing 20 kg (44 lb) or more: 20 mg taken once per day

Omeprazole will be administered as a gastro-protectant against corticosteroid therapy.

## Gene Therapy for Achromatopsia (CNGA3)

---

7. Prednisolone or Prednisone (oral steroid) as prophylaxis against potential intraocular immune responses:

- 0.5 mg/kg daily for one week **prior** to ATIMP administration
- 1mg/kg daily for the first week following ATIMP administration
- 0.5mg/kg daily for the second week following ATIMP administration
- 0.25mg/kg daily for the third week following ATIMP administration
- 0.125mg/kg daily for the fourth week following ATIMP administration

All Non- Investigational Medicinal Products (NIMPs) are licensed within the EU and US and will be procured from standard hospital stock.

Sites will maintain a system that allows adequate reconstruction of NIMP movements and permits recording of which participants received which NIMPs during the trial, with an evaluation of the compliance where necessary.

### 5.4.2 Protocol defined clinical schedule

#### 5.4.2.1 Baseline Assessments

A detailed assessment of visual function and retinal imaging of both eyes will be performed preoperatively as outlined in Section 5.6 (Table 2: Trial Assessments). For assessments requiring multiple baselines, testing is preferred on separate days within a maximum 9-month period to allow for day-to-day variation and test-retest variability for individual participants. However, it is acknowledged that a pragmatic balance will be achieved for what is appropriate for the different tests on an individual basis. Each set of baseline measurements may take up to 5 days to perform in total. Where it is not possible to obtain reliable data for any given baseline assessment, further protocol defined timepoints for those assessments will not be taken, unless required for evaluation of safety. In some instances, results for protocol specified baseline tests may be available as a part of routine clinical examination within 9 months. As such, if the subject provides informed consent to use the results from the previously conducted tests, then these assessments will not need to be repeated at baseline.

Visual assessment results will be sent for reading and analysis to independent reading centres within the UK and US. For both UK and US sites imaging with OCT, fundus autofluorescence and fundus photography will be reviewed by the site teams but also sent for independent analysis by the Reading Centre, Queens University, Belfast, Ireland, during the course of the trial. Adaptive optics images will be sent to the Medical College of Wisconsin, US, for reading. Octopus perimetry will be sent to the Oregon Health and Science University Casey Eye Institute, US, reading centre. Photoaversion videos will be sent to MeiraGTX and their research development partners. All images will be saved under pseudo-anonymised patient identifiers and surgical images will only be taken of the patient's eye to ensure that patients remain unidentified. Images and videos obtained during photoaversion testing may reveal some facial characteristics. To the extent possible, images and videos will be anonymised by removing any personally identifiable information from the imaging or video files.

Up to 10 mL of blood will be sampled in order to assess baseline levels of circulating antibodies against AAV8 and of circulating antibodies against rAAV serotype 8 so that immunological responses to vector capsids can be determined following ATIMP administration (collectively described as serology in Table

## **Gene Therapy for Achromatopsia (CNGA3)**

---

2: Trial Assessments). We anticipate that that majority of participants will have no detectable pre-existing circulating antibodies against AAV8. The presence or absence of circulating antibodies will not affect recruitment of the participant. All serology tests will be performed at a laboratory approved by the sponsor and their research development partners. There is wide variability in the abilities of individual children to perform certain of the proposed investigations; the evaluations for children will be restricted to those tests that individuals are able to perform reliably.

Tests that will be performed in all participants are:

- Serological tests
- Blood pressure
- Haematology
- Biochemistry
- Ocular examination
- Colour fundus photography
- Spectral Domain Optical coherence tomography (SD-OCT)
- Fundus Autofluorescence (FAF) imaging
- Best corrected visual acuity
- At least one of static perimetry and / or full-field stimulus testing.
- Light-sensitivity (Photoaversion) testing

Tests that will be performed where possible unless lack of patient co-operation or equipment/facilities are:

- Contrast sensitivity
- Reading assessment
- Colour vision testing
- Adaptive optics (AO) imaging
- QOL questionnaires

Further details of clinical assessments can be found in the Gene Therapy for Achromatopsia (CNGA3) study manual. Images taken at all timepoints will be sent for independent reading and analysis at centres in both the UK and US.

### (i) Ocular examination and retinal imaging.

Ocular examination using slit lamp biomicroscopy will assess the anatomical integrity of the eyes and allow quantification of intraocular inflammation. During the examination, intraocular pressure will be determined by tonometry.

Retinal imaging includes colour fundus photography, fundus autofluorescence (FAF) imaging, SD-OCT, and adaptive optics (AO) imaging. FAF imaging allows visualisation of the retinal pigment epithelium (RPE) by taking advantage of its intrinsic fluorescence derived from its lipofuscin content. SD-OCT

## **Gene Therapy for Achromatopsia (*CNGA3*)**

---

imaging enables measurement of retinal thickness and provides information about the integrity of the layers of the retina. AO imaging provides direct visualization of the photoreceptor mosaics *in vivo*.

### (ii) Functional and Participant-Related Outcome Assessments.

Where possible the participant will complete an age appropriate Impact of Visual Impairment (IVI) vision-specific quality of life questionnaire, and EQ5D-5L questionnaire and EQ5D-Y questionnaire, or equivalent as appropriate. Reading ability including reading acuity, maximum reading rate, and critical print size will be assessed where possible.

The degree of light sensitivity (photoaversion) will be investigated in two ways (i) Objectively by measurement of palpebral aperture narrowing in response to gradually increasing light intensity and (ii) Subjectively by participant reported symptomatology.

Best-corrected ETDRS visual acuity will be measured in each eye. Contrast sensitivity will be measured using the Pelli-Robson chart.

Colour vision will be assessed comprehensively using plate tests and computerised tests probing colour discrimination along all 3 axes of colour.

Retinal sensitivity will be determined using static perimetry and/or full field stimulus testing (FST) where possible.

Full-field electroretinography (ERG) and pattern ERG (PERG) will be performed according to the International Society for Clinical Electrophysiology of Vision (ISCEV) standards to assess both generalised retinal (rod and cone systems) and isolated macular function. Modified ISCEV protocols may be necessary in young children using internationally recognised modified protocols. For young children, this procedure may be performed under general anaesthesia.

ERG data will be analysed and interpreted by dedicated full-time Clinical Visual Electrophysiology Consultants with extensive experience and who are directly involved in defining ISCEV standards.

### **5.4.2.2 ATIMP administration Procedures**

The protocol describes the intended surgical technique for ATIMP administration. The surgical procedure may be modified on a case-by-case basis in the interests of safety; any modification will be documented in the operation notes and eCRF. Consent to record the surgery will be requested of the participant. Intraocular surgery will be recorded by video via the operating microscope as described in the consent process. Relevant anonymised video recordings and images will be stored alongside the trial database, with the sponsor and held by third party vendors.

#### **5.4.2.2.1 Pre-operative Procedures**

For prophylaxis against potential intraocular immune responses to the ATIMP, participants will be prescribed a course of oral prednisolone as described in section 5.4.1.5.

Preoperative procedures and intraocular administration of ATIMP will be as described in the Gene Therapy for Achromatopsia (*CNGA3*) study manual.

## Gene Therapy for Achromatopsia (CNGA3)

---

### 5.4.2.2.2 Technique for intraocular administration of ATIMP

The choice of eye for ATIMP administration will be the poorer-seeing eye as identified by the participant and CI/PI taking into account ocular dominance and visual acuity.

The recombinant vector will be delivered in the form of a suspension of viral vector particles injected intraocularly (subretinally) under direct observation using an operating microscope. This procedure will involve a 3-port pars plana vitrectomy followed by injection of ATIMP using a fine cannula through small retinotomies into the subretinal space.

Surgery will be performed under general anaesthesia. The eye and face will be prepared using povidone iodine solution as per routine intraocular surgery. The face and eye will be covered with an adhesive sterile plastic drape. An opening will be made at the point of the palpebral fissure and a wire speculum inserted to retract the upper and lower eyelids. The speculum and all intraocular instruments will be sterilised according to standard local operating procedures. Three pars plana sclerotomies will be sited to enable intraocular infusion, endoillumination probe and surgical instruments. The fundus will be viewed by means of a binocular indirect ophthalmic microscope (BIOM) viewing system or a contact lens. To minimise the possibility of unplanned retinal detachment or preretinal fibrosis, vitrectomy (aspiration of vitreous gel) will be performed using a disposable cutter.

Intraocular administration of the viral vector suspension (AAV8-hG1.7p.coCNGA3) will be performed using a subretinal cannula advanced through the retina. Under direct visualisation, the ATIMP will be injected under the neurosensory retina, causing a localised retinal detachment with a self-sealing non-expanding retinotomy/retinotomies. The aim will be to target the ATIMP to the central macula. If appropriate, the bleb of ATIMP will be manipulated to the target area using a fluid-air exchange. The site and extent of the subretinal bleb of ATIMP suspension will be documented by video recording.

Following intraocular administration of ATIMP, the retinal periphery will be examined for any unplanned retinal breaks for appropriate management by retinopexy with or without intraocular tamponade at the discretion of the operating surgeon. Intraocular instruments used subsequent to ATIMP delivery are disposable and will be destroyed after a single use. Sclerotomies may be secured using a vicryl suture. Standard doses of cefuroxime antibiotic and betamethasone will be administered subconjunctivally as prophylaxis against postoperative infection and inflammation respectively. Bupivacaine will be administered for analgesia. The surgical procedure may be modified on a case-by-case basis in the interests of safety; any modification will be documented in the operation notes and CRF.

On the basis of our own experience, we anticipate that the subretinal ATIMP bleb will resolve spontaneously during the first 48 hours.

Surgery may be performed, as is conventional for intra-ocular procedures, on a day-case basis and participants will be managed subsequently as out-patients, although hospital-based accommodation may be used for convenience.

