### 4.1.6 Explanation for Choice of Comparators

There is no currently approved treatment for Achromatopsia caused by mutations in *CNGA3*. The comparator will be the contralateral eye and supplementary data collected as part of a prospective, parallel natural history study of patients with Achromatopsia.

The totality of the data from paediatric subjects enrolled in the UK and adult subjects enrolled in the U.S. will be reviewed and inform the design of a future Phase II interventional study.

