## 5.6 Trial Assessments

Table 2: Trial assessments

	Screening	Baseline 			ATIMP admin	D1	D3	W1	W2	W4	W6	W12	W24
Flexibility of schedule ( $\pm$ days)		- 9 months			Day 0	$\pm$ 0D	$\pm$ 1D	$\pm$ 2D	$\pm$ 4D	$\pm$ 7D	$\pm$ 7D	$\pm$ 14D	$\pm$ 14D
Visit number	1	2	3	4	5	6	7	8	9	10	11	12	13
Informed consent	•												
Physical exam	•												
Medical history	•												
Eligibility determination	•												
ATIMP administration					★								
Adverse event review		•	•	•	•	•	•	•	•	•	•	•	•
Concomitant medication review	•	•	•	•	•	•	•	•	•	•	•	•	•
Genetic screening 	•												
Pregnancy test	•				•								
Vital signs 	•	•				•		•	•	•			
Haematology 		•				•		•	•	•			
Biochemistry/glucose/liver and renal function 		•				•		•	•	•			
Serology		•								•		•	•
PCR						•				•			
QoL questionnaires (IVI and EQ5D-5L, or equivalent)		•											•
Visual acuity 	•	•	•	•		•	•	•	•	•	•	•	•
Colour vision assessments		•	•	•								•	•
Contrast sensitivity		•	•	•								•	•
Reading assessments		•	•	•								•	•
Static perimetry		•	•	•								•	•
Full Field Stimulus Testing		•	•	•								•	•
Ocular examination	•	•	•	•		•	•	•	•	•	•	•	•

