**CNGA3CNGA3 Gene Therapy trial for Achromatopsia**

	Screening	Baseline 			ATIMP admin	D1	D3	W1	W2	W4	W6	W12	W24
Flexibility of schedule ( $\pm$ days)		- 9 months			Day 0	$\pm$ 0D	$\pm$ 1D	$\pm$ 2D	$\pm$ 4D	$\pm$ 7D	$\pm$ 7D	$\pm$ 14D	$\pm$ 14D
Fundus photography		•				•	•	•	•	•	•	•	•
Optical coherence tomography	•	•	•	•		•	•	•	•	•	•	•	•
Adaptive optics imaging		•	•										•
Fundus autofluorescence		•	•									•	•
Pattern Electroretinography 	•												•
Full field Electroretinography 	•												•
Photoaversion/ light sensitivity assessments (test and questionnaires)		• 	• 	• 								• 	• 

 Baseline assessments may be performed on the same day where considered logistically and clinically appropriate

 If result is available from prior testing, no repeat test mandated. Result will be reported into the CRF.

 Measurements for vital signs include: blood pressure, pulse, respiration rate, arterial oxygen saturation, temperature, height and weight

 Hematology to include the following parameters: Haemoglobin, Haematocrit, Erythrocytes, Mean Corpuscular Volume, Mean Corpuscular Haemoglobin, Platelet, Leukocytes, Absolute Neutrophils, Absolute Lymphocytes, Absolute Neutrophils, Absolute Eosinophils, Absolute Basophils

 Biochemistry to include the following parameters: Sodium, Potassium, Chloride, Bilirubin, Alkaline Phosphatase, Aspartate Aminotransferase, Alanine, Aminotransferase, Lactate Dehydrogenase, Gamma Glutamyl Transferase, Total Protein, Albumin, Calcium, Magnesium, Phosphate, Urea/BUN, Urate, Creatinine, Glucose

 Visual acuity at day 1 and 3 will be assessed using the previous refraction.

 ERG assessments may be performed under general anaesthesia if necessary.

 Photoaversion Questionnaire only to be completed at one baseline visit, "Photoaversion Device Questionnaire – Baseline" to be completed after every PA assessment

 "Photoaversion Device Questionnaire – after Surgery" to be used at week 12 and week 24 straight after Photoaversion assessments.

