#### 3.2. Baseline

In general, baseline is defined as the closest visit prior to ATIMP administration and will exclude any screening observations (unless there are no other observations prior to ATIMP administration). However, for efficacy parameters with multiple planned assessments in the baseline window, the arithmetic mean will be used as the baseline value.

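### Nothing keeps the acuity readings used to choose the poorer-seeing eye out of the baseline mean, so regression to the mean may bias acuity change

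*Protocol*

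**What the plan says.** **Choice of eye.** Protocol 5.4.2.2.2: "The choice of eye for ATIMP administration will be the poorer-seeing eye", and it continues "as identified by the participant and CI/PI taking into account ocular dominance and visual acuity". No visit or reading is named.

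**Acuity before treatment.** Table 2 in Protocol 5.6 schedules visual acuity once at screening and at each of three baseline visits. Protocol 5.4.2.1 says "For assessments requiring multiple baselines, testing is preferred on separate days within a maximum 9-month period", while footnote 1 to Table 2 allows "Baseline assessments may be performed on the same day where considered logistically and clinically appropriate". Protocol 5.3.1.6, 5.3.1.6.2 and 5.4.2.1 also let consented routine results from the preceding 9 months stand in for screening or baseline tests.

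**Baseline value.** SAP 3.2 says that baseline "will exclude any screening observations (unless there are no other observations prior to ATIMP administration", and that "for efficacy parameters with multiple planned assessments in the baseline window, the arithmetic mean will be used as the baseline value".

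**Use of the fellow eye.** Protocol 4.1.6: "The comparator will be the contralateral eye", together with natural history data. SAP 6.1 plans individual plots of the treated against the untreated eye, descriptive summaries (by study eye when appropriate), and an optional repeated-measures model of treated-eye change adjusted for baseline. SAP 1.2 plans no hypothesis test.

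**The concern.** When two eyes see about equally well, the one that measures worse is worse partly by chance. If the readings that pointed to it are also averaged into baseline, its baseline is too low and the fellow eye's is too high. Later readings carry fresh error, so both eyes drift back: the treated eye appears to gain and the fellow eye appears to lose, with no treatment effect.

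The eye-selection rule appears under administration procedures, after the baseline assessments, so baseline acuities would ordinarily be at hand when the eye is chosen. Protocol 5.4.2.3 makes acuity one of the two principal assessments for safety and efficacy. The trial has up to 18 participants, and its data are meant to inform a Phase II design. In that setting, opposite shifts of a few letters in the two eyes could be read as a small benefit.

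**Working it through.** The plan gives no sample size calculation, acuity SD or bias figure, so there is nothing of its own to reproduce.

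**Inputs**
- k = 3 baseline acuities per eye, taken as independent (Protocol Table 2; SAP 3.2 averages them).
- s = test-retest SD per eye per visit. Protocol 5.4.2.1 acknowledges this variability but does not quantify it. Assumed 2 to 7 letters.
- D = SD of the true difference between the eyes, centred on zero. Not given. Assumed 0 to 10 letters.
- Choice rests on the lower three-visit mean alone. This is the case with the most reuse, not something the protocol states.

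**Formula.** The measurement error in the between-eye difference of baseline means has variance v = 2s²/k. Choosing the lower eye on that difference gives an expected error of

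between-eye bias = √(2/π) × v / √(D² + v)

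Half falls on the treated eye (upward) and half on the fellow eye (downward).

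**Worked case, s = 5.** v = 2 × 25 / 3 = 16.67.
- D = 0: 0.798 × √16.67 = 3.26 between eyes, 1.63 in the treated eye.
- D = 5: 0.798 × 16.67 / √41.67 = 2.06 between eyes, 1.03 in the treated eye.

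**Range (letters, treated eye / between eyes)**

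| s | D = 0 | D = 5 | D = 10 |
|---|---|---|---|
| 2 | 0.65 / 1.30 | 0.20 / 0.40 | 0.10 / 0.21 |
| 3 | 0.98 / 1.95 | 0.43 / 0.86 | 0.23 / 0.46 |
| 5 | 1.63 / 3.26 | 1.03 / 2.06 | 0.62 / 1.23 |
| 7 | 2.28 / 4.56 | 1.72 / 3.43 | 1.13 / 2.26 |

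If same-day repeats shared all their error, the three readings would act as one (k = 1). The same formula then gives 0.31 to 3.95 in the treated eye and 0.61 to 7.90 between eyes.

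**Other ways of choosing** (simulation, 400,000 pairs per case, no treatment effect; s = 5, D = 5)
- Three-visit baseline mean: +1.02 treated, −1.02 fellow, 2.04 between eyes, in line with the formula.
- Screening and baseline readings pooled: 0.82 treated, 1.63 between eyes.
- Half of the choices unrelated to acuity error: 0.53 treated, 1.05 between eyes.
- Screening acuity only, or dominance unrelated to acuity error: about zero for both (within 0.03 letters in every case run).

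**Baseline adjustment.** In the three-visit case, the mean change adjusted to the average baseline is 1.02 letters, the same as the raw mean change. There is no untreated group in the treated-eye model against which the drift could be separated, so the optional model does not remove it.

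**Sustained-improvement criterion (Protocol 5.10.3.3).** Taking a gain above 2s at two follow-ups as the threshold (assumed, because the protocol does not quantify baseline variation), the chance of meeting it with no effect rises from about 0.5% to 0.6–0.8%.

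**The case against.** A reader might infer that the plan uses the same acuity to choose the eye and to form baseline. The documents do not say so. They name no visit, they bring in the participant's view and ocular dominance, and a separate screening acuity exists that SAP 3.2 leaves out of baseline when other values are available. If that reading alone guided the choice, the bias is already about zero. This stands, and the point is therefore conditional.

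A reader might also infer that a doubled bias enters a planned between-eye estimate. It does not: SAP 6.1 specifies plots and summaries, the optional model covers the treated eye only, and nothing is tested. The doubling affects how plots are read and any contrast computed later. The effect on the sustained-improvement criterion is also minor.

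Nor do the larger figures represent the whole range. Values of about 2.0 to 4.6 letters between eyes (s = 3 to 7) require truly equal eyes. A real, stable difference between the eyes causes no bias in change from baseline, so the poorer-eye rule is not itself at fault.

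What remains is that no provision separates the deciding readings from the baseline, and neither document mentions regression to the mean. Allowing routine results to serve for screening or baseline means that one reading could do both jobs.

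**Conclusion.** The point holds in conditional form and is minor. The documents do not say which acuity readings inform the choice of eye, and nothing keeps those readings out of the baseline mean. If baseline acuities are used, treated-eye acuity change is biased upward by about 0.1 to 2.3 letters and a between-eye reading by about 0.2 to 4.6 letters. These figures rest on assumed SDs (s 2 to 7, D 0 to 10), three independent baseline readings, and choice on their mean alone. Correlated same-day repeats would raise them; participant judgement or dominance would lower them. Which case applied cannot be told from the documents, because they do not require the deciding readings to be recorded.

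**What to change.** Keep the poorer-eye rule and those who apply it. Add to the protocol that the study eye, and the acuity readings seen when choosing it, are recorded before the acuity readings that form baseline are taken. SAP 3.2 already drops screening values when others exist, so baseline would then be independent of the choice. State also that one prior routine result may not serve as both screening and baseline acuity.

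SAP 1.2 describes dosing in the past tense, so some eyes may already have been chosen. For participants whose eye was chosen later, or changed for clinical reasons, add a sensitivity acuity summary with baseline taken only from readings not used in the choice. Where no such reading exists, or the record does not show which were used, state regression to the mean as a limitation of the treated-eye and between-eye results.

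The cost is a short protocol addition and one table from data already collected. The choice may rest on fewer acuity readings, and the sensitivity baseline will be less precise.
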